## **10.4.2** Contraception Guidance

This study does include Woman of Childbearing Potential (WOCBP) and accordingly these women must use highly effective contraception during the entire study participation. Reference is made to Section 10.4.3 in the unlikely event that a pregnancy is detected during the study.

#### CONTRACEPTIVESa ALLOWED DURING THE STUDY INCLUDE:

**Highly Effective Methods**b **That Have Low User Dependency** *Failure rate of*  $\leq 1\%$  *per year when used consistently and correctly.* 

- Intrauterine device without hormonal release (IUD)
- Bilateral tubal occlusion
- Azoospermic partner (vasectomized or due to a medical cause)

Azoospermia is a highly effective contraceptive method provided that the partner is the sole sexual partner of the woman of childbearing potential and the absence of sperm has been confirmed. If not, an additional highly effective method of contraception should be used. Spermatogenesis cycle is approximately 90 days.

Note: documentation of azoospermia for a male partner can come from the site personnel's review of the participant's medical records, medical examination, or medical history interview.

**Highly Effective Methods**b **That Are User Dependent** *Failure rate of* < 1% *per year when used consistently and correctly.* 

#### Sexual abstinence

Sexual abstinence is considered a highly effective method only if defined as refraining from heterosexual intercourse during the entire period of risk associated with the study intervention. The reliability of sexual abstinence needs to be evaluated in relation to the duration of the study and the preferred and usual lifestyle of the participant.)

- a) Contraceptive use by men or women should be consistent with local regulations regarding the use of contraceptive methods for those participating in clinical studies.
- b) Failure rate of < 1% per year when used consistently and correctly. Typical use failure rates differ from those when used consistently and correctly.

The table below presents contraceptive methods that are **not** considered highly effective and these should **not** be used during the study.

10 MAY 2023 Page: 80 of 97

#### CONTRACEPTIVES NOT ALLOWED DURING THE STUDY INCLUDE:

**Effective Methods That Are Not Considered Highly Effective** Failure rate of  $\geq 1\%$  per year when used consistently and correctly.

- Male or female condom with or without spermicide
- Cervical cap, diaphragm, or sponge with spermicide
- A combination of male condom with either cervical cap, diaphragm, or sponge with spermicide (double-barrier methods)c

Note: Periodic abstinence (calendar, symptothermal, postovulation methods), withdrawal (coitus interruptus), spermicides only, and lactational amenorrhea method (LAM) are not acceptable methods of contraception.

## **10.4.3** Collection of Pregnancy Information:

- The investigator will collect pregnancy information on any female participant who becomes pregnant while participating in this study. The initial information will be recorded on the appropriate form and submitted to the sponsor within 24 hours of learning of a participant's pregnancy.
- The participant will be followed to determine the outcome of the pregnancy. The investigator will collect follow-up information on the participant and the neonate and the information will be forwarded to the sponsor. Generally, follow-up will not be required for longer than 6 to 8 weeks beyond the estimated delivery date. Any termination of pregnancy will be reported, regardless of fetal status (presence or absence of anomalies) or indication for the procedure.
  - While pregnancy itself is not considered to be an AE or SAE, any pregnancy complication or elective termination of a pregnancy for medical reasons will be reported as an AE or SAE.
  - A spontaneous abortion (occurring at <22 weeks gestational age) or still birth (occurring at >22 weeks gestational age) is always considered to be an SAE and will be reported as such.
- Any post-study pregnancy related SAE considered reasonably related to the study
  intervention by the investigator will be reported to the sponsor as described in
  Section 8.3.4. While the investigator is not obligated to actively seek this
  information in former study participants, he or she may learn of an SAE through
  spontaneous reporting.
- Any female participant who becomes pregnant while participating in the study will discontinue study intervention or be withdrawn from the study.

## 10.5 Appendix 5: Liver Safety Actions and Follow-up Assessments

## 10.5.1 Liver safety -related monitoring and discontinuation criteria

Investigators and participants should pay special attention to non-specific symptoms which may be associated with liver dysfunction; including anorexia, nausea, fatigue, right upper abdominal discomfort, vomiting, malaise, jaundice, fever, and rash.

10 MAY 2023 Page: 81 of 97

- Information on these symptoms should be asked for in case of abnormal liver laboratory values (Table 10-2) or any other suspicion of liver dysfunction.
- Participants should be regularly reminded to contact the investigator immediately if they are concerned about such symptoms, and unscheduled visits for evaluation should be considered
- In the case of increased liver values as defined in Table 10-2, a retest should be performed within 72 hours of the initial test results. If the abnormal liver values are confirmed in the retest, liver safety monitoring should be initiated.

Table 10-2: Liver Safety-Related Monitoring and Discontinuation Criteria

Lab result	Measures
ALT or AST > 3 x ULN	Initiate close observation as defined in Section 10.5.2.
AP > 2 x ULN b	Consider withdrawal of study intervention if the participant does not adhere to procedures required for close observation a Initiate close observation as defined in Section 10.5.2. Consider withdrawal of study intervention if the participant does not adhere to procedures required for close observation
ALT or AST > 3 x ULN and TBL > 2 x ULN	Withdraw study intervention and initiate close observation as defined in Section 10.5.2.
ALT or AST > 3 x ULN and INR > 1.5 x ULN	Withdraw study intervention and initiate close observation as defined in Section 10.5.2.
ALT or AST > 3 ULN with appearance of fatigue, nausea, vomiting, right upper abdominal quadrant pain or tenderness, fever, rash and/or eosinophilia (>5%)	Withdraw study intervention and initiate close observation as defined in Section 10.5.2.
ALT or AST > 5 x ULN for more than 2 weeks ALT or AST > 8 x ULN	Withdraw study intervention and initiate close observation as defined in Section 10.5.2. Withdraw study intervention and initiate close observation as
ALI OF A OLIV	defined in Section 10.5.2.

ALT = alanine aminotransferase; AP = Alkaline phosphatase; AST = aspartate aminotransferase; INR= international normalized ratio, TBL = total bilirubin, ULN = upper limit of normal (all referring to serum/plasma) a in case visits for close observation could not be arranged with a frequency deemed adequate by the investigator, despite of reasonable efforts

# 10.5.2 Close observation of participants with liver function test findings

- Abnormal laboratory results and clinical signs and symptoms resulting in close liver observation should be reported as adverse event.
  - Any increase in liver enzymes meeting the following criteria needs to be reported as an adverse event to the sponsor within 24 hours of the investigator's awareness for expedited reporting to the health authorities:
    - ALT and/or AST >8x ULN OR
    - ALT and/or AST >3x ULN with total bilirubin >2x ULN
  - The investigator may consider whether the observed increase in liver values would qualify as SAE (see Section 8.3.6).

<sup>b Close observation can be stopped if bone AP value is reported as abnormal

10 MAY 2023 Page: 82 of 97

- It is critical to initiate close observation immediately upon detection and confirmation of early signals of possible drug-induced liver injury, and not to wait until the next scheduled visit or monitoring interval
- Procedures to be taken resemble workup/ documentation along the guideline of the US FDA for assessment of potential drug-induced liver injury (FDA Guidance for Industry 2009). Objectives are to:
  - o Ensure participant safety
  - o Identify possible non-study-intervention-related causes of liver injury
- A close observation has to be initiated during intervention or follow-up phase if liver function tests meet the criteria in Table 10-2. Close observation includes:
  - o Sampling for the first batch of laboratory parameters (Table 10-3).
  - Repeating follow-up samplings (Table 10-3) 2 to 3 times per week.
     Frequency of retesting can decrease to once a week or less if abnormalities stabilize.
  - o Obtaining a detailed history of the symptoms and prior or concurrent diseases
  - Obtaining a history of concomitant drug use (including nonprescription medications and herbal and dietary supplement preparations), alcohol use, recreational drug use, and special diets.
  - Ruling out acute viral hepatitis, autoimmune or alcoholic hepatitis, nonalcoholic steatohepatitis, hypoxic/ischemic hepatology and biliary tract disease. Unless an obvious and firm non-drug induced liver injury diagnosis has already been made additional procedures, e.g. ultrasound examinations should be performed. If requested, tests will be done retrospectively using residual blood/serum samples collected at visits before laboratory abnormalities occurred.
  - o Obtaining a history of exposure to environmental chemical agents
  - Obtaining additional tests to evaluate liver function as required (e.g. INR, direct bilirubin measurements)
  - o Considering gastroenterology or hepatology consultations
- Data for any findings are to be recorded in the corresponding eCRF pages
- Stopping criteria for close observation:
  - 2 consecutive normal/baseline results for liver enzymes in addition to availability of results from detailed close liver observation lab panel, related procedures, relevant medical and medication history and the reporting of signs and symptoms related to elevated liver enzymes, or
  - o a confirmed clinical diagnosis explaining the elevated liver enzymes, or
  - if fragmentation reveals abnormal bone AP as reason for the increase of AP>2 x ULN.

Table 10-3 lists the samples to be taken during close observation for liver safety. The samples are to be taken as needed.

10 MAY 2023 Page: 83 of 97

Table 10-3: Samples during close observation for liver safety

First batch of parameters to be taken when initiating close observation for liver safety a
Albumin
Alkaline phosphatase (AP)
Alanine-aminotransferase (ALT)
Aspartate-aminotransferase (AST)
Bone-specific alkaline phosphatase (BALP)
Complete blood count including WBC with differentials
Cholinesterase
Conjugated (direct) bilirubin
Creatine kinase (CK)
GGT
Hemoglobin
INR
Lactate dehydrogenase (LDH)
PT
Total bilirubin
HDL-cholesterol
LDL-cholesterol
Total cholesterol
Triglycerides
Anti-hepatitis A virus IgM antibodies.
Hepatitis B virus surface antigen (if positive, automatically test below antibodies related to
HBV and HDV)
- Anti-hepatitis B surface antibodies
- Anti-hepatitis B core total antibodies
- Anti-hepatitis B IgM antibodies
- Hepatitis B PCR (viral copies)
- HDV antibodies (if positive, automatically test HDV RNA)
Anti-HCV antibodies
Hepatitis C RNA
Anti-HDV antibodies (if positive, automatically test HDV RNA)
Anti-HEV IgM (if positive, automatically test HEV RNA)
Anti-cytomegalovirus IgM antibodies
Anti-Epstein-Barr Virus IgM antibodies
HSV IgM (anti-HSV IgM)
IgG level (gamma globulins)
IgA
IgM
c-Antineutrophil cytoplasmic antibodies
c-Antineutrophil perinuclear antibodies
Anti-mitochondrial antibodies Anti-nuclear antibodies
Anti-Indicieal antibodies  Anti-Smooth muscle antibodies
A1AT level
Ceruloplasmin
Ferritin
Iron
Total iron binding capacity
Total from binding capacity
Follow-up samples during close observation for liver safety b
Albumin
Alkaline phosphatase
· · ·
Alanine-aminotransferase
Aspartate-aminotransferase
WBC with differentials
Cholinesterase
Creatine kinase
Conjugated (direct) bilirubin

10 MAY 2023 Page: 84 of 97

Table 10-3: Samples during close observation for liver safety

Total bilirubin
Gamma-glutamyl transferase
INR
LDH

- a) First sample after AST or ALT > 3 X ULN or AP>2xULN
- b) Additional parameters/tests may be added as medically justified
- A1AT = Alpha-1 antitrypsin; GGT = Gamma-glutamyl transferase; INR = International normalized ratio; HBV = hepatitis B virus; HCV = Hepatitis C virus, HDL = high-density lipoprotein; HDV = hepatitis D virus; HEV = hepatitis E virus; HSV = herpes simplex virus; IgA = immunoglobulin A; IgG = immunoglobulin G; IgM = immunoglobulin M, LDH = lactate dehydrogenase; LDL = low density lipoprotein; PCR = Polymerase chain reaction; PT = prothrombin time; RNA = ribonucleic acid; ULN = Upper limit of normal; WBC = White blood cell count

10 MAY 2023 Page: 85 of 97

# **10.6** Appendix 6: Prohibited concomitant medications

Table 10-4: Prohibited concomitant medication potentially confounding efficacy

Prohibited from the time shown until 1 week after the last dose of study drug		
	Hormonal therapies	
From 1 week prior to Baseline Visit	Vaginal hormonal products (rings, creams, gels)	
From 4 weeks prior to Baseline Visit	Transdermal estrogen alone or estrogen/progestin products	
From 8 weeks prior to Baseline Visit	
 
Oral estrogen and/or progestin therapy
 
Intrauterine progestin therapy
 
	
From 12 weeks prior to Baseline Visit	Progestin implants and estrogen alone injectable drug therapy	
From 24 weeks prior to Baseline Visit	Estrogen pellet therapy or progestin injectable drug therapy	
	Non-hormonal therapies	
From 12 weeks prior to Baseline Visit	adjuvant endocrine therapy other than tamoxifen, aromatase inhibitors or GnRH analogues (e.g., CDK 4/6 inhibitor, toremifene, fulvestrant). The participant is allowed to switch to CDK 4/6 inhibitors after 12 weeks of treatment with the study intervention (i.e., after the placebo-controlled period ends).	
From 4 weeks prior to Baseline Visit	Antidepressant drugs:  Participants are permitted to continue to use antidepressant drugs and over the counter/herbal treatments (see details below) when the dose has been stable for at least 4 weeks and when it is anticipated to be stable for the duration of the study. In addition, the drug has been prescribed solely for the management of another disorder (e.g., neuropathic pain, depression).  Participants are not allowed to start with these drugs during the study:  • Anti-depressant drugs with effect on vasomotor symptoms (e.g., paroxetine, other including selective serotonin reuptake inhibitors, serotonin norepinephrine reuptake inhibitors and tri-cyclic antidepressants, alpha agonists [clonidine], methyldopa, gabapentin, pregabalin, medicinal cannabis or derivatives)  • Over the counter/herbal treatments including traditional Chinese medicine for treatment of vasomotor symptoms.  Others:  • Oxybutynin/ Oxybutynin hydrochloride	

CDK = Cyclin-dependent kinases, CYP2D6 = Cytochrome P450 2D6, GnRH = Gonadotropin-releasing hormone

10 MAY 2023 Page: 86 of 97

[figure not shown]
[figure not shown]

Table 10-6 and Table 10-7 list examples of the most common medication regarded as

10 MAY 2023 Page: 87 of 97

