**Follow-Up:** The treatment phase will be followed by a 4-week safety follow-up period in participants who do not continue with the treatment extension (part C) and completed with the FU visit.

**Treatment extension (part C):** Participants who completed 52 weeks of treatment and decide to continue in the study will receive 120 mg (2x 60 mg soft gel capsules) of elinzanetant orally once daily. Treatment in part C will start the day after last medication intake in the main study, i.e., without interruption of treatment.

**Follow-Up (part C):** The treatment extension (part C) will be followed by a 4-week safety follow-up period and completed with the FU part C visit.

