# 7. Discontinuation of Study Intervention and Participant Discontinuation/Withdrawal

# 7.1 Discontinuation of Study Intervention

It may be necessary for a participant to permanently discontinue study intervention. If study intervention is permanently discontinued, and if the investigator considers it medically justified, the participant may remain in the study without receiving the study intervention. As a general rule, all procedures scheduled for the end-of-treatment visit should be performed at the time of premature discontinuation of study intervention and documented. In case this is considered not medically appropriate for certain procedures (e.g. for invasive procedures if only short time has elapsed since the last scheduled assessment) this should be documented by the investigator. All scheduled study visits and procedures, except for study intervention, should continue if agreed by the participant. PK sampling is also not required. For participants who agree to continue in the study, any medication used after discontinuation of study intervention must be documented.

Treatment extension (part C):

Participants who prematurely discontinue from treatment during part C are asked to return to the EoT part C and FU part C visit.

For withdrawal from study see Section 7.2.

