# 8.1 Efficacy Assessments

In this clinical trial, efficacy will be assessed using clinical outcome assessments. As these are responded to by the study participants themselves, they are considered PROs. The PROs used in the study are described in Section 8.1.1

Planned time points for all efficacy assessments are provided in the SoA (Section 1.3).

The efficacy assessments described in Section 8.1.1 are not conducted during treatment extension (part C) of the study.

10 MAY 2023 Page: 43 of 97

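### Table 10-4's efficacy-based bar on starting or changing VMS-active antidepressants runs through Part C, where efficacy is not assessed; and Sections 4.1 and 8.2.11 give different AE rules for suicidal ideation

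*Protocol*

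**What the plan says.** **Prohibited medication.** Table 10-4 in Protocol 10.6 is titled "Prohibited concomitant medication potentially confounding efficacy", and its period is "Prohibited from the time shown until 1 week after the last dose of study drug". In the antidepressant row, a drug already in use for another disorder may continue "when the dose has been stable for at least 4 weeks and when it is anticipated to be stable for the duration of the study". For antidepressants with an effect on vasomotor symptoms (SSRIs, SNRIs, tricyclics and some related agents), "Participants are not allowed to start with these drugs during the study". The visible table has one release tied to a time point, in the endocrine-therapy row: "The participant is allowed to switch to CDK 4/6 inhibitors after 12 weeks of treatment with the study intervention".

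**Part C.** Section 4.1 says: "Treatment in part C will start the day after last medication intake in the main study, i.e., without interruption of treatment". The synopsis takes the extension to Week 156. Section 8.1 says: "The efficacy assessments described in Section 8.1.1 are not conducted during treatment extension (part C) of the study". Section 8 rules out waivers.

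**Suicidal ideation.** A BDI-II item 9 answer of 2 or 3 triggers an email to the investigator. Section 4.1 then has suicidal ideation of any kind reported as an adverse event. Section 8.2.11 has the investigator weigh, from the clinical picture, whether an adverse event report is warranted. Both are current text.

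**The concern.** A restriction justified by its effect on an efficacy measurement should end when the measurement ends. If it does not, it limits treatment for no stated purpose. The treatment here is for depression, in women who may stay on study drug for three years and whose depression Section 8.1.1.6 says to treat by local practice. A site that follows local practice and prescribes an SSRI in Part C commits a deviation.

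The second half concerns the safety data. If two sections give different reporting rules for the same questionnaire answer, the number of suicidal-ideation events in the treatment-emergent tables depends partly on which section a site follows.

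**Working it through.** The plan states no figure on this point, so the check is a comparison of sections plus week arithmetic.

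**Does the bar reach Part C?**

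1. Table 10-4 ties the end of the bar to the last dose of study drug and forbids new starts during the study.
2. Section 4.1 continues elinzanetant into Part C without a gap, and Section 4.4 counts a participant as having completed the study only after all phases. Part C is therefore part of the study.
3. Neither Table 10-4 nor Section 6.8.2 exempts Part C. Sections 7.1, 7.1.2, 7.1.3, 7.1.5.1 and 7.2 each state their own Part C rule, so silence in Table 10-4 is not an exemption.
4. The Amendment 2 summary lists the sections changed to add the extension. Section 10.6 is not among them, which suggests an oversight.

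**How long does it run without its stated purpose?**

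- End of the bar for a Part C completer: 156 + 1 = Week 157.
- Part C on study drug: 156 − 52 = 104 weeks.
- Share of the longest treatment period: 104 / 156 = 66.7%.
- Part C visits (Table 1-3): T14, T15, T16, T17, EoT and FU = 6, none with a Section 8.1.1 instrument.

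Part B differs: Table 1-2 still schedules the hot flash diary around Weeks 25–26, 35–36 and 49–50, so the efficacy reason holds to the end of the main study.

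**Does any analysis need the bar in Part C?** SAP 4.1.2 flags intercurrent events only to Day 84. SAP Table 6-5 treats the antidepressant groups as intercurrent events only if started, changed or stopped in the first 12 weeks. Protocol 9.5 has Part C analysed and reported separately.

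**The two adverse event rules.**

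| Situation | Section 4.1 | Section 8.2.11 |
|---|---|---|
| Item 9 answer of 2 or 3, ideation clinically confirmed | Report | Judgement, in practice report |
| Item 9 answer of 2 or 3, no matching clinical presentation | Report | Judgement, may not be reported |

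The rules part in the second row. The Amendment 2 summary shows that 8.2.11 is the newer rule: it leaves interpretation of a 2 or 3 to the investigator. That summary lists 4.1 for the extension but not for this change.

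**Where it can occur.** Post-baseline BDI-II visits (Table 1-2): T2, T4, T6, T7, T9, T11, T13/EoT and FU = 8. Footnote e removes FU for women entering Part C, so 8 − 1 = 7 for them. Three of these visits (T2, T4, T6) fall in the placebo-controlled 12 weeks. The BDI-II is a Section 8.1.1 instrument and is not collected in Part C.

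**The case against.** **No rule forces a choice between the antidepressant and elinzanetant.** A reader might infer that a Part C woman must forgo the drug or stop study treatment. The documents do not say so. The stopping rules in 7.1 to 7.1.5 cover pregnancy, liver tests, platelets and recurrent intolerable adverse events, not prohibited medication. Table 3-2 treats prohibited medication as an intercurrent event separate from permanent discontinuation. Section 7.2 allows withdrawal for compliance reasons, but at the investigator's discretion. This objection stands: the consequence is a deviation that cannot be waived.

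**Nor is stopping shown to cost more in Part C.** A reader might infer this from Section 7.1: "Participants who prematurely discontinue from treatment during part C are asked to return to the EoT part C and FU part C visit". A woman who stops in the main study may stay in follow-up, but she also loses access to Part C, which is offered only to those who complete 52 weeks of treatment. The comparison does not run clearly one way.

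**Parts of 10.6 are not visible.** Two figures are missing, the sentence introducing Tables 10-6 and 10-7 is cut off, and the Table 10-4 footnote defines CYP2D6 although no visible row uses it. Section 8.5 says CYP2D6 converts tamoxifen to its major active metabolite. A drug-interaction reason for restricting some listed agents therefore cannot be excluded. This stands as a limit on confidence and shapes the fix, but the visible table gives efficacy as its only reason.

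**The CDK 4/6 release is weak support.** It concerns cancer therapy, and no other visible row has a comparable release. Antidepressants are not singled out, and the argument does not depend on this comparison.

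**The reporting conflict is narrow.** Suicidal ideation is not an event of special interest, the SAP has no dedicated analysis of it as an adverse event, and the item answers are stored electronically whatever is reported. All of this is right. It limits the consequence but leaves two current instructions that disagree.

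**Conclusion.** Both halves hold, and both are minor.

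- **Part C.** By its wording the bar on starting or changing these antidepressants covers 104 weeks, 67% of the longest possible treatment period, in which its only stated purpose does not apply. Confidence is moderate. It rests on reading the last dose of study drug as including Part C doses, and on no unseen part of 10.6 supplying another reason. Psychotherapy, unlisted drugs and antidepressants already at a stable dose remain available. The documents give no rate of new antidepressant need, so no number of affected women can be stated.
- **Suicidal ideation.** Sections 4.1 and 8.2.11 conflict for an item 9 answer of 2 or 3 without a matching clinical presentation, at up to 8 post-baseline visits (7 for women entering Part C). Confidence is high. How often such answers occur is unknown.

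No primary or key secondary efficacy result is affected by either half.

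**What to change.** 1. Add one sentence to the antidepressant row of Table 10-4: *In Part C, an antidepressant that the investigator judges necessary may be started or its dose changed, unless it is barred for drug-drug interaction, including any CYP2D6 concern with tamoxifen.* The main-study bar stays as it is.
2. Replace the adverse event sentence in Section 4.1 with the Section 8.2.11 wording, so that sites have one rule.

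The cost is two sentences in a protocol amendment. No SAP change and no new data collection are needed, because Section 6.8 already records reason, dates and dose of concomitant drugs. The price is slight added confounding of Part C adverse events, for example somnolence or fatigue. That is acceptable, since Part C has no control arm and women on stable antidepressants may already take part.
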